7.1.2 Secondary study parameters/endpoints (if applicable)

- 1) mortality at day 28 and week 12 of therapy due to fungal infection, overall mortality at 28 days and 12 weeks.
- 2) resolution of neutropenic fever, defined as percentage of patients with a oral temperature of $<38\text{ }^{\circ}\text{C}$ at day 7 of voriconazole treatment [17]; time (in days) to resolve fever is also noted.
- 3) percentage of voriconazole serum concentrations within the targeted window of 2-5mg/L during therapy based on repeated measurements in time.
- 4) percentage switched to salvage therapy (i.e. amphotericin B or one of its lipid or liposomal formulations; or echinocandin (e.g., caspofungin/anidulafungin) or other triazole (e.g., posaconazole); or measured concentration level in control arm during treatment for toxicity or failure)

- 5) side effects (visual disturbance and liver enzymes) Side effects leading to drug discontinuation.
- 6) time (in days) of to global response as defined under the primary endpoint definition after the start of voriconazole
- 7) The evaluation of cost-effectiveness (hospital and societal per perspective) of voriconazole TDM in patients with invasive aspergillosis will be an integral part of this project.

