4.4 Sample size calculation

In a previous randomized trial with voriconazole in a dosage according to product leaflet with similar inclusion criteria the response was: complete in 20%, partial in 30%, stable in 10% and failure in 40% [16]. As TDM will probably result in the largest benefit in patient with low voriconazole trough levels, who are not responding, or in patients with high trough levels, who stopped because of side effects, the sample size calculation of this study is based on the reduction of patients failing on voriconazole therapy. For control patients (treated without TDM) a failure rate of 40% is expected [16], while for patients during the experimental TDM episode, a failure of 20% is expected. Under the most unfavourable assumption that the intra cluster correlation coefficient equals the intra period correlation coefficient varying between 0.002 and 0.02, and knowing that at least 12 centres are participating in this study, each cluster must include 16 patients to obtain a power of about 80% with an unreliability of 5% (two-sided) to detect a clinically relevant improvement of 20% of reduction of patients failing on voriconazole at day 28 of treatment compared to control. This means that in total 192 patients are necessary for performing this study. To compensate for loss during follow-up in total 200 patients will be included. Loss during follow-up is defined as patients not willing to continue participation because of personal reasons. Patient stopping because of voriconazole adverse effects are noted as "failure".

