6.5 Description and justification of route of administration and dosage

See attached 1B brochure for route of administration for both groups and for starting dosage in both group (6mg/kg IV bid; 400mg PO bid) and for maintenance dose in control group (4mg/kg IV bid; 200mg PO bid)

As in daily practice serum concentration levels are measured for toxicity or therapeutic failure, the attending physician may request a concentration level. This request is subjected to a protocol: toxicity (rise in liver enzymes > 5 times upper level of normal values, after starting voriconazole), failure (no clinical, microbiological or radiological response after 7 days of treatment with voriconazole).

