7.3 Study procedures

- 1) At day two of fever the patients is informed about the study and a 24 hour period is given to think of participation.
- 2) The haematologist, in consultation with a medical microbiologist or infectious diseases specialist, will decide to start voriconazole therapy in a patient with suspected IA based on EORTC/MSG criteria. A HRCT scan is crucial part of the procedure for diagnosing the invasive fungal disease. Triggers for ordering an HRCT include detection of galactomannan in serum or plasma, pulmonary complaints or abnormalities seen on X-ray and unexplained fever of > 4 days despite broad-spectrum antibiotic therapy. A HRCT is performed at start of voriconazole treatment +/- 3 days.
- 3) Voriconazole serum concentrations after the 5th dosage (IV 6mg/kg for the first 24 hours followed by 4mg/kg bid, PO 400mg for the first 24 hours followed by 200mg bid) will be measured in all patients during treatment with voriconazole during the TDM period. Two blood samples will be drawn, one immediately before the dose (t= 0) and one 2h after the dosage (t=2) when administered orally or 1h after the end of infusion

when administered intravenously. If the serum trough level is < 2.0 mg/L the dosage will be increased. If the serum trough level is > 5mg/L the dosage will be reduced. Dosage adjustment will be performed according to a standard algorithm. Also a sample (5ml) will be drawn to assess CYP450 2C9 and 2C19 polymorphisms.

- 4) Three days after dosage adjustment a control sample series is drawn, followed by the same dose adjustment algorithm.
- 5) After reaching the therapeutic window trough levels, surveillance samples will be drawn twice a week while the patient is in the hospital. For outpatient treatment trough levels will be drawn at regular visits of the patients to the outpatient clinic (about once every two weeks). Since outpatients are clinically more stable, fluctuations are expected to be less frequent, moreover patients are often put on voriconazole during hospital stay and have a stable level when leaving the hospital. In the period without TDM, serum samples will be stored and used later to evaluate serum trough levels during the standard care episode. During this period, no additional vena punctures will have to be performed for the purpose of the study as the blood samples will be taken during regular sampling on the morning round. In total 16-54ml will be drawn depending on the duration of treatment.

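### Secondary endpoint 4 counts a requested voriconazole level as a switch to salvage therapy in the control arm only, so its comparison favours TDM by construction

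*Protocol*

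**What the plan says.** Section 7.1.2, item 4, defines the endpoint as the "percentage switched to salvage therapy". It lists amphotericin B and its lipid or liposomal forms, an echinocandin, or another triazole. The same bracket then adds "or measured concentration level in control arm during treatment for toxicity or failure".

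Section 6.5 explains how such a level arises: "As in daily practice serum concentration levels are measured for toxicity or therapeutic failure, the attending physician may request a concentration level". It names two triggers. One is toxicity, meaning a liver-enzyme increase beyond five times the normal limit once the drug has been started. The other is "failure (no clinical, microbiological or radiological response after 7 days of treatment with voriconazole". The day-7 limit belongs to the second trigger only.

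In the TDM period, section 7.3 states that concentrations "will be measured in all patients during treatment with voriconazole during the TDM period", and the dose is adjusted on them. Item 4 counts none of these measurements. Routine control samples are stored and evaluated later (7.3), so in controls only a level requested for cause creates an event.

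**The concern.** A measured level is not a change of drug, and it can add events to one arm only. Take two patients with the same liver-enzyme rise or the same lack of response at day 7, both kept on voriconazole. The control patient whose level is requested has reached endpoint 4. The TDM patient, whose level is measured anyway, has not. The two percentages therefore do not measure the same thing.

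At stake is a significant secondary result for TDM, labelled as fewer switches to salvage therapy, when drug switching did not differ. Nothing else in the protocol guards against this. Treatment is open-label, the request is at the physician's discretion, and the blinded expert panel (section 3) reviews the primary endpoint and secondary endpoints 1, 2, 5 and 6, but not 4. Section 7.1.2 does not ask for the drug switches to be shown apart from the measured levels.

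**Working it through.** **Patients per arm.** The protocol gives no figure for endpoint 4, so its sample size (4.4) is used only to fix the number per arm. The inputs are 40% v 20% failure, two-sided 5%, about 80% power, at least 12 centres with 16 patients each, and a correlation of up to 0.02.

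- Without clustering: n = [1.960·√(2·0.30·0.70) + 0.842·√(0.24 + 0.16)]² / 0.20² = 81.2, so 82 per arm.
- With 8 patients per cluster-period, correlation 0.02 within a period and 0 between periods, the design effect is 1 + 7·0.02 = 1.14. Then 82·1.14 = 93.5, so 94 per arm and 188 in total.
- The stated 192 is within 3% of this. Equal periods give 192/2 = 96 per arm, with 81.4% power.

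**Size of the artefact.** Let s be the true switch rate, the same in both arms, and q the share of non-switching controls with a requested level.

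- TDM rate: p_T = s
- Control rate: p_C = s + (1 − s)q
- Expected difference: (1 − s)q, never negative and zero only if q = 0

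**Chance of a significant result favouring TDM.** P = Φ[(p_C − p_T)/SE − 1.960], with SE = √{[p_C(1 − p_C) + p_T(1 − p_T)]/96}. Clustering is ignored. For s = 20%:

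- q = 5%: p_C = 24%, SE = √(0.3424/96) = 0.0597, P = Φ(0.670 − 1.960) = 10%
- q = 10%: p_C = 28%, SE = √(0.3616/96) = 0.0614, P = Φ(1.304 − 1.960) = 26%
- q = 20%: p_C = 36%, SE = √(0.3904/96) = 0.0638, P = Φ(2.509 − 1.960) = 71%

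Because the protocol gives neither s nor q, a range follows. Each cell shows the excess in points and P.

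| s | q = 5% | q = 10% | q = 20% | q = 30% |
|---|---|---|---|---|
| 10% | 4.5; 16% | 9; 43% | 18; 90% | 27; >99% |
| 20% | 4; 10% | 8; 26% | 16; 71% | 24; 96% |
| 30% | 3.5; 8% | 7; 18% | 14; 53% | 21; 86% |

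A pooled variance lowers these chances by about one point at most.

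**With clustering.** If endpoint 4 had the design effect of 1.14, the effective number would be 96/1.14 = 84.2 per arm. The three chances for s = 20% become about 9%, 23% and 65%.

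**Without the clause.** Both rates equal s, the expected difference is 0, and the chance of a significant result favouring TDM returns to the nominal 2.5%. Counting measured levels in both arms would not help, because every TDM patient would then be an event.

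**The case against.** The best defence is that a level requested for cause in a control patient is a partial crossover to the tested strategy, and that counting it as escape is a recognisable composite. Dropping it also has a price: requested levels might avert some drug switches in controls and so hide part of a TDM effect. This explains the clause but does not cure it, because a TDM patient with the same trigger has no matching event.

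A second defence concerns size. Both triggers select patients who may well be switched to another drug, and those already count. Only controls who are measured and not switched add to the excess, so q could be small; at q = 5% and s = 20% the excess is 4 points. This stands, and it limits what can be said about size, but not about direction. An unseen analysis plan might report the components separately, but the endpoint as defined here would still be one-sided.

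A reader might infer three stronger points, which the protocol does not support:

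- *That 6.5 contradicts 4.4, where controls are described as treated without TDM, and that power is therefore lower.* TDM in this protocol means scheduled sampling in all patients with algorithm-driven dose adjustment. Section 6.5 presents requested levels as daily practice, so they belong to the standard-care comparator. It does not say that the algorithm is applied to controls, and nothing in the protocol yields a control failure rate other than 40%.
- *That the cost-effectiveness result inherits the bias.* The Summary expresses that ratio per therapeutic failure prevented, not per endpoint 4 event, and 7.1.3 takes costs from the resources used. No text links item 4 to the economic analysis.
- *That the primary endpoint is touched.* The global response in 7.1.1 does not use the clause.

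**Conclusion.** The point holds for secondary endpoint 4 alone. The direction follows from the text: the clause can only raise the control percentage, so the comparison favours TDM unless no non-switching control has a requested level. Since 6.5 describes such requests as usual practice, q = 0 is unlikely.

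The size is illustrative. It rests on assumed values of s and q, a common true switch rate, 96 patients per arm, and a test of the composite as written. Over s = 10–30% and q = 5–30%, the excess runs from 3.5 to 27 points and the chance of a significant result favouring TDM from about 8% to over 99%, before any allowance for clustering.

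This should be fixed before analysis. It is one of seven secondary endpoints, and it does not threaten the trial's main result.

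**What to change.** In 7.1.2, item 4, define the endpoint identically in both arms as a switch to another antifungal drug from the list already given, and delete the control-arm level clause. Report separately the percentage of controls with a level requested under 6.5, by trigger, as a measure of contamination. A reader can then judge how far monitoring reached the control periods.

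The cost is one deleted clause and one added descriptive line. Both pieces of information are already needed for the endpoint as written, so no further data collection is required. Patient care, the primary endpoint and the sample size do not change. Any switches that requested levels avert in controls remain part of the comparison of TDM with standard care.

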Rationale: Patients with haematological malignancies and chemotherapy induced prolonged neutropenia are at risk for severe bacterial and fungal infections. These opportunistic infections can result in prolonged hospital stay, increases costs and greater mortality. Voriconazole has now been recommended as the first line agent for invasive pulmonary aspergillosis (IA). Retrospective observational studies of voriconazole serum concentration suggest that serum concentration correlate with toxicity and clinical response. These observations were however made in small series of patients and data were collected retrospectively. These inherent methodological flaws make it impossible to draw definite conclusions about the effect of voriconazole serum concentration monitoring on the outcome of IA, and therefore considered insufficient proof to recommend voriconazole concentration determination in blood as standard of care. The impact that so-called serum concentration guided dosing of voriconazole will have on treatment success can only be evaluated through a prospective randomized clinical trial.

Objective: The objective of this study proposal is to determine whether pharmacologic optimization of voriconazole by means of therapeutic drug monitoring (TDM) results in improved patient outcomes (efficacy and safety) and is more cost-effective compared to the current standard of care.

Study design: we designed a prospective stratified cluster randomized cross-over trial of therapeutic drug monitoring in patients with haematological disease who have developed IA. The order of periods (TDM or standard of care, each 12 months) will be randomized per centre.

Study population: Patients with haematological malignancies and possible, probable or proven IA according to EORTC criteria.

Intervention (if applicable): In the intervention group the voriconazole dosage will be adjusted to achieve trough blood concentrations in a predefined window of 2-5 mg/L. In the control group voriconazole will be dosed according to product leaflet.

Main study parameters/endpoints: The primary clinical endpoint will be a global response consisting of a combined endpoint of toxicity and response to therapy (clinical, microbiologic and radiologic responses) 28 days after starting treatment with voriconazole. A sample size of n=192 is needed to detect a 20% absolute reduction in the number of

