Voriconazole is the first line treatment of IA among patients with haematological malignancies and hematopoietic stem cell transplant recipients according to recent international guidelines [43] as reported in a large randomised trial [16]. Recent observational studies suggest that voriconazole serum concentrations of at least 1 to 2.0 mg/L are associated with improved clinical outcome [18, 19, 42]. This clinical finding is supported by the in-vitro susceptibility of *Aspergillus fumigatus* to voriconazole [20]. On the other hand high trough concentrations exceeding 5 mg/L are associated with toxicity, mainly neurological and hepatotoxicity [40, 42,46]. It has also been shown that the inter-individual variation of voriconazole plasma levels is significant due to hereditary factors that influence the rate of clearance of the drug. Consequently, the guidelines for the treatment of IA published recently by the Infectious Diseases Society of America (IDSA) recommend monitoring of voriconazole concentration levels and adjusting dosage accordingly as an option for patients not responding to the standard weight-based dosing of voriconazole. This may be caused by sub-therapeutic serum concentrations or treatment discontinuation due to side effects that might be caused by toxic serum concentrations. Monitoring of serum

concentrations and adjusting the dose will be an alternative to switching to other antifungal agents such as a lipid formulation of amphotericin B, caspofungin or posaconazole [43].

Furthermore, voriconazole treatment is relatively expensive itself (€400/day for parenteral treatment) and suboptimal use can be expected to result in therapeutic failure, and additional costs incurred by the need for more expensive salvage antifungal therapy and prolonged hospital stay. We hypothesize that dosing of voriconazole based on serum concentration (so-called therapeutic drug monitoring) will result in improved clinical outcome of patients with IA, by reducing the risk of therapeutic failure and toxicity and that this will be cost-effective [39, 41, 43]. A multi-center randomized controlled clinical trial was designed to test this hypothesis [21, 22, 41].

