3. STUDY DESIGN

As the number of patients treated for invasive aspergillosis in each hospital is limited, a multi centre set up is required to have a study powered to detect a clinically relevant difference in outcome between the intervention group and the control group. For this study a cluster randomized design - instead of a randomisation at patient level - was chosen to minimize logistic problems, optimize inclusion of patients and limit bias during the study. Blinding the intervention would increase the costs of the study considerably without providing better results. The cross-over design was chosen to diminish influences by centre, as the inter-centre variability in facility and treatment can influence outcome of treatment. Differences which are found can now be attributed solely to the intervention as the centre serves as its own control. As this study will be performed in several centres with random start with standard care or with TDM-tailored treatment, we anticipate that the time-based biases will be negligible. To diminish the carry-over effect from one period to the next a wash-out period of 28 days is established, which equals the time of start of treatment until evaluation on the primary endpoint. This prevents that two treatment protocols, intervention and control are operational at the same time. For these reasons we choose a cluster randomized cross-over design in which every cluster receives both interventions during two consecutive periods (TDM and standard care, 12 months each). This longitudinal design was previously successfully used in the Netherlands [32]. Randomization by a computer-generated randomization system determines the sequence within in each cluster. In this way the variability between clusters is taken into account, this results in an improved power. The randomization will be stratified to obtain equally balanced clusters with respect to experience and size. At six months, inclusion will be evaluated and it will be estimated whether duration per period has to be increased or decreased and whether the clusters are still balanced. The intervention (TDM) consists of taking serum samples at day three of treatment, measuring the voriconazole serum levels and adjusting the dosage to reach the therapeutic window. Dosing of voriconazole will be done during the control period according to the product brochure.

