Response to treatment will be evaluated at day 7 (fever), day 28 (primary endpoint) and at 12 weeks after start of therapy (mortality). Assessment of quality of life will be performed after release from the hospital at different time points (2 weeks, 3 months, 6 months and 1 year). Cost effectiveness from hospital perspective will be evaluated after release from the hospital. Cost effectiveness from societal perspective will be evaluated after 1 year after start of the treatment.

An expert panel (EPHO) of three specialists in the field of haemato-oncology, radiology, and mycology, and who are unaware of allocation to either of the two arms of the study (intervention or control), will classify all documented aspergillosis according to the EORTC/MSG criteria [33,45] and will report the likelihood whether fever was caused by: drug fever (e.g. cytarabine), mucositis, malignancy, Graft –Versus-Host Disease, or infection and a likelihood whether mortality was caused by fungal infection or progression of malignancy or any other cause, using protocol-defined criteria. Likelihood will be presented on a scale of 0/3 till 3/3. The evaluation of endpoints by an independent expert panel excludes investigators' bias [34, 35]. At the end of the study the EPHO, unaware of allocation to either of the two arms of the study (intervention or control), will review each patient on the primary and the following secondary endpoints 1, 2, 5 and 6. After the review of the independent expert panel the multi disciplinary study team, consisting of haematologists, infectious diseases specialists, radiologists, pharmacists, medical microbiologists, a biostatistician and a MTA expert will analyze the data on all endpoints using the outcome of the pre-screening of the expert panel.

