8.2 Adverse and serious adverse events

Adverse events are defined as any undesirable experience occurring to a subject during a clinical trial, whether or not considered related to the investigational drug. All adverse events reported spontaneously by the subject or observed by the investigator or his staff will be recorded.

A serious adverse event is any untoward medical occurrence or effect that at any dose results in death;

- is life threatening (at the time of the event);
- requires hospitalisation or prolongation of existing inpatients' hospitalisation;
- results in persistent or significant disability or incapacity;
- is a congenital anomaly or birth defect;
- is a new event of the trial likely to affect the safety of the subjects, such as an unexpected outcome of an adverse reaction, lack of efficacy of an IMP used for the treatment of a life threatening disease, major safety finding from a newly completed animal study, etc.

All SAEs will be reported to the accredited METC that approved the protocol, according to the requirements of that METC.

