8.4 Data Safety Monitoring Board (DSMB)

An independent expert panel (EPHO) of three specialists in the field of haemato-oncology, radiology, and mycology, and who are unaware of allocation to either of the two arms of the study (intervention or control), will classify all documented aspergillosis according to the EORTC/MSG criteria. This independent expert panel will also be involved in safety follow up (toxicity differences between the two arms) and premature termination of the study (grade A1 evidence that TDM of voriconazole improves outcome).

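### Secondary endpoint 5 leaves out non-visual neurological side effects that do not stop voriconazole, although the protocol names neurological toxicity as a main toxicity of high troughs

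*Protocol*

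**What the plan says.** The Summary states the aim as finding out whether TDM "results in improved patient outcomes (efficacy and safety) and is more cost-effective compared to the current standard of care", so safety is part of the question. The Introduction supports the upper limit of the target window by saying that "high trough concentrations exceeding 5 mg/L are associated with toxicity, mainly neurological and hepatotoxicity".

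Section 7.1.2, item 5, sets the side-effect endpoint: "side effects (visual disturbance and liver enzymes) Side effects leading to drug discontinuation". The second half carries no limit by type of side effect. Under section 3 the expert panel, blinded to arm, "will review each patient on the primary and the following secondary endpoints 1, 2, 5 and 6", so this endpoint is in its remit. Section 8.4 also gives the panel a part in following toxicity differences between the arms.

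The general rule in section 8.2 is: "All adverse events reported spontaneously by the subject or observed by the investigator or his staff will be recorded". Treatment is open label; section 3 gives as the reason: "Blinding the intervention would increase the costs of the study considerably without providing better results".

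**The concern.** TDM is meant to prevent two kinds of toxicity, and the endpoint names only one of them in full. Hepatotoxicity is covered by liver enzymes whether or not treatment continues. Neurological toxicity is represented by visual disturbance; any other neurological event enters only through the discontinuation clause.

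That clause depends on a treatment decision as well as on toxicity. If the two periods offer different ways of dealing with the same event, the proportion that ends in stopping may differ even when the event rates are equal. Fewer stops under TDM could be a real benefit, but the endpoint could not tell fewer neurological events from fewer stops for the same events.

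**Working it through.** **1. Named toxicities against the endpoint.**

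| Side effect | Introduction, troughs above 5 mg/L | Endpoint 5, drug continued | Endpoint 5, drug stopped |
|---|---|---|---|
| Hepatic | named | counted | counted |
| Visual | not mentioned separately | counted | counted |
| Other neurological | within the named neurological toxicity | **not counted** | counted |

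One cell is empty. The mismatch is confined to non-visual neurological events in patients who stay on voriconazole.

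**2. Why that cell may fill differently by period.** In the TDM period (sections 6.6 and 7.3, Appendix 1) troughs are measured routinely and a trough above 5 mg/L leads to a lower dose. In the control period dosing follows the product leaflet. Section 6.5 lets the physician request a level for liver enzymes above 5 times the upper limit of normal, or for no response after 7 days. No neurological trigger is listed, and stored control samples are evaluated later. Level-guided reduction is therefore routine in one period only.

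**3. What the endpoint measures.** Let e be the proportion of patients with a non-visual neurological event and f the share of those events that stop the drug (C control, T TDM). The toxicity question is e_C − e_T. Endpoint 5 compares e_C·f_C − e_T·f_T. With equal event rates e, the endpoint still shows e·(f_C − f_T). The protocol gives neither e nor f, so every value below is an assumption:

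| e in both arms | f_C = f_T | f_C = 0.50, f_T = 0.25 | f_C = 0.75, f_T = 0.25 |
|---|---|---|---|
| 10% | 0 | 2.5 points | 5 points |
| 20% | 0 | 5 points | 10 points |
| 30% | 0 | 7.5 points | 15 points |

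Example: 20% × 0.50 = 10% against 20% × 0.25 = 5%, with no difference in events.

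**4. Information lost when the share is the same in both arms.** The protocol gives no sample size for this endpoint. Its total is 12 centres × 16 = 192 (section 4.4). That total reproduces for the primary endpoint: 82 per arm for 40% against 20%, times a design effect of 1 + 7 × 0.02 = 1.14 (8 patients per centre-period, no gain from between-period correlation), times 2 = 187. This is 15.6 per centre, rounded up to 16. Equal periods give n = 192/2 = 96 per arm.

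With clustering ignored, power = Φ{[|p1 − p2| − 1.96·√(2p̄(1 − p̄)/n)] / √([p1(1 − p1) + p2(1 − p2)]/n)}, where p̄ is the mean of p1 and p2. For 20% against 10%: (0.100 − 0.101)/0.051 = −0.02, so power is 0.49.

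| Assumed event rates | All events counted | 75% stop | 50% stop | 25% stop |
|---|---|---|---|---|
| 20% vs 10% | 0.492 | 0.375 | 0.259 | 0.147 |
| 30% vs 10% | 0.940 | 0.835 | 0.638 | 0.355 |

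Counting only the events that stop the drug loses information in every row. How much depends on rates that the protocol does not give.

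**The case against.** The best defence is that little is lost. Discontinuation for any side effect is counted, neurological ones included. Section 4.4 notes stopping for adverse effects as failure, and the Summary puts toxicity into the primary endpoint. Section 8.2 records every event that is volunteered or seen by staff, and a blinded panel reviews endpoint 5. The CRF, to which section 7.1.3 refers for detail, is not shown and may ask about neurological symptoms. Visual disturbance may have been meant to stand for neurological toxicity.

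Most of this stands, and it rules out several stronger readings that a reader might draw:

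- *The endpoint counts only visual disturbance and liver enzymes.* It does not; the second half of the line adds treatment-stopping side effects of any kind.
- *The trial cannot answer its safety question.* Hepatic, visual, treatment-stopping and all recorded adverse events can be compared between arms.
- *Safety data rest on spontaneous reports.* Section 8.2 includes staff observation, is not stated to be the source for endpoint 5, and liver enzymes are laboratory values. Open-label reporting of symptoms may still differ at site, and a panel cannot review what was never recorded, but the protocol does not show that this happens.
- *The out-of-window figures size the gap.* On the Introduction's percentages, 10–25% of 96 (9.6 to 24) controls exceed 5 mg/L, and 25–60% of 96 (24 to 57.6) TDM patients would be below 2 mg/L if the same distribution applied. These are patients with out-of-window levels, not neurological events.
- *Dose reduction exists only under TDM.* The product leaflet is not shown and may deal with intolerance. Only level-guided reduction can be said to be routine in one period alone.

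What the defence does not remove is the empty cell. An event recorded under section 8.2 is still not part of endpoint 5 unless it is visual, hepatic or stops the drug. Nowhere does the protocol say that visual disturbance represents neurological toxicity as a whole.

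**Conclusion.** The point holds in a narrow form. The Introduction and section 7.1.2 do not match: neurological toxicity is one of two main reasons for the 5 mg/L limit, and its non-visual, non-stopping part is missing from the prespecified side-effect endpoint. Counting such events only when the drug is stopped may capture them differently by arm. That is plausible from the dosing sections but not demonstrated.

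The size is unknown. The contrasts of 0 to 15 percentage points and the power losses above rest wholly on assumed event rates and stopping shares, equal arms of 96 and no clustering. No figure in the protocol changes, and the primary endpoint's sample size is not affected. This is a cheap improvement to one secondary endpoint, not a threat to the trial.

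**What to change.** Reconcile the Introduction with section 7.1.2 by rewording item 5 to: *visual disturbance, other neurological events and liver enzymes, whether or not voriconazole is discontinued; and, separately, any side effect that leads to discontinuation*. Take the neurological events from the adverse events already recorded under section 8.2, and state that they belong to the blinded panel's review of endpoint 5.

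If symptoms are also to be asked about, ask the same questions on fixed calendar days that are identical in both periods, for example at the day 7 and day 28 evaluations. Do not tie them to blood sampling. TDM patients are sampled again after each dose adjustment and then twice a week in hospital, while no control sampling frequency is stated, so questioning at sampling could itself favour detection in one arm.

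The cost is one changed line, a little more CRF and panel work, and a slightly higher recorded event rate in both arms. No blood draw is added and no treatment rule changes.
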